## 13. RISK/BENEFIT ASSESSMENT

### 13.1. RISKS

The use of the Tack Endovascular System in percutaneous transluminal balloon angioplasty (PTA) may result in anticipated potential risks or complications similar to other available endovascular implant devices (such as stents) used in PTA procedures. Such risks are included in the Tack Endovascular System Instructions for Use (IFU) and are listed below:

- Access failure or abrupt closure
- Allergic / anaphylactoid reaction to anticoagulant and/or antithrombotic therapy or contrast medium
- Allergic reaction to nitinol
- Amputation of lower extremity
- Anemia
- Angina / coronary ischemia / myocardial infarction
- Arrhythmia
- Arterial occlusion / (re) stenosis / dissection / thrombus
- Arterial spasm
- Arteriovenous fistula
- Blue toe syndrome
- Claudication or rest pain, worsened
- Death
- Disseminated intravascular coagulation
- Edema, peripheral
- Embolism
- Emergent repeat hospital intervention
- Fever
- Gangrene
- Gastrointestinal bleed from anticoagulation / antiplatelet medication
- Hematoma / hemorrhage
- Hypotension / hypertension
- Inadvertent venipuncture
- Infection / abscess at insertion site
- Inflammation
- Multi-organ failure
- Pain
- Pseudoaneurysm
- Renal insufficiency or failure
- Respiratory distress or failure
- Septicemia / bacteremia (sepsis)
- Tack implant embolization
- Tack implant migration (device moves over time)
- Tack implant occlusion / restenosis

- Tissue necrosis
- Trauma to adjacent structures
- Stroke / TIA (hemorrhagic / embolic)
- Vascular complications which may require surgical repair

These risks are present in any endovascular treatment procedure for which the study subjects would be indicated because of their disease and will be reviewed with all subjects during the informed consent process.

### 13.2. POTENTIAL BENEFITS

Prior human studies validated that the Tack Endovascular System can safely and effectively appose dissected tissue in subjects with post-PTA dissections, thereby resulting in acute dissection repair and long term luminal patency.

### 13.3. JUSTIFICATION FOR CLINICAL STUDY

The safety and performance of the Tack Endovascular System has been established through extensive design verification and validation testing, including prior human use, and through a detailed risk analysis process per ISO 14971. The results of non-clinical and clinical testing have demonstrated safety and benefit and therefore, it is anticipated that the assessment of risk and benefit is appropriate for the intended use of the study device and the initiation of this study.

This trial is being conducted in order to collect additional safety and effectiveness data on the Tack Endovascular System device to support a Premarket Approval (PMA) application. All efforts will be made to minimize the occurrence of risk to study subjects through investigator/institution qualification, investigator training on the safe and proper use of the device in accordance with the IFU, investigator/site training on the protocol, and clearly defining subject eligibility requirements (inclusion/exclusion criteria) and contraindications as described in the IFU.

## 14. ADVERSE EVENT REPORTING

The adverse event (AE) reporting period will begin at the time of enrollment into the study (See **Section 10.3.1**) and will continue through study completion.

The Principal Investigator at each participating site is ultimately responsible for the timely review and reporting of adverse events per respective IRB/EC policy and in accordance with FDA requirements. All Adverse Events during the safety observation period should be followed until the event is resolved or judged to be chronically stable. Follow-up information will be submitted to the Medical Monitor and/or the Sponsor as it becomes available.

All adverse events must be recorded on the Adverse Event CRF by the Investigator (or designee). The report should include: severity, duration, action taken, treatment outcome and relationship of the adverse experience to the study device, procedure, concomitant medications, pre-existing condition, (i.e., unrelated, related or relationship unknown).

All events will be made accessible to the Sponsor and/or designee to review the need for FDA regulatory reporting. All AE's will be reviewed for their relationship to the study device(s) and/or procedure and severity of the event.

Severity of adverse events will be classified according to the following criteria:

**Mild:** A mild adverse event is an AE usually transient in nature and generally not interfering with normal activities.

**Moderate:** A moderate adverse event is an AE that is sufficiently discomforting to interfere with normal activities.

**Severe:** A severe adverse event is an AE that is incapacitation and prevents normal activities.

The relationship of the AE to the device or procedure will be classified according to the following criteria:

**Unrelated:** No relationship to the study device or study procedure.

**Possibly:** Signs or symptoms are the study device or study procedure *and* the natural disease process or other injury/illness.

**Definitely:** Clearly related to the study device and/or study procedure. Signs and symptoms not related to natural disease process or other injury/illness.

**Unknown:** Unable to determine relationship between study device, study procedure, natural disease process and/or other injury/illness.

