## 8.4. SCREENING SUCCESS AND FAILURE CRITERIA

Final eligibility of a subject will occur during the Index Procedure. Subjects undergoing an angiographic screen must provide prior informed consent. Every effort will be made to ensure eligibility of the participants prior to enrollment. If no angiographic exclusion criteria are met after pre-enrollment angioplasty, subjects will be considered eligible for enrollment. If at any point prior to or just after pre-enrollment angioplasty, an angiographic exclusion criteria is met, subjects will not be considered eligible for enrollment and will be documented as

“angiographic screen failures”. No further follow-up will be required of these subjects, however; reason for angiographic failure shall be documented by the site into a screening log.

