## 10.2. PRE-ENROLLMENT BALLOON ANGIOPLASTY

All consented subjects undergoing balloon angioplasty for possible enrollment into this study shall receive PTA treatment with a standard balloon or FDA-approved Lutonix drug-coated balloon.

Note: Requirements for pre-dilatation with a standard balloon (non-drug coated) preceding treatment with a DCB should be performed in accordance with the respective IFU. Once the DCB is introduced, inflations should be performed according to recommendations below for balloon angioplasty. Operators should follow these recommendations unless patient safety concerns present.

The recommendations for balloon inflation are as follows:

- The operator should select a balloon diameter that can be inflated to a ratio of 1.1:1 relative to the target lesion proximal RVD.
- The length of the balloon should be appropriate for the lesion length. When possible, a single balloon should be selected that extends across the entire lesion. If a DCB is being used, then the relevant instructions for use should be referenced for lesion lengths requiring multiple balloons.
- Balloon Inflation: Inflate the balloon and maintain inflation at the specified 1.1:1 diameter for a minimum of 60 seconds total (180 seconds is recommended).

Please refer to the Instructions for Use (IFU) for detailed instructions regarding Pre-Enrollment Balloon Angioplasty inflation recommendations.

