#### 10.3.1. ENROLLMENT (INTENT-TO-TREAT)

A subject is defined as an intent-to-treat (ITT) patient and officially enrolled in the study once the Tack Endovascular System is advanced through the introducer sheath. Subjects in whom at least one Tack is not placed, will be exited after 12 months. Subjects in whom at least one Tack is placed will be followed for 36 months.

In addition, the per-protocol (PP) population will be defined as ITT subjects with evaluable data that have met the definition for device success, excluding subjects with major deviations such as:

- A major inclusion/exclusion criterion deviation; or
- A major procedural deviation

The criteria for deviations meeting the classification of “major” will be defined before study endpoint data is available for statistical analysis. All major deviations will be adjudicated by an independent designee without visibility to study results.

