Per-protocol (PP) subjects	
The per-protocol (PP) population is defined as ITT subjects with evaluable data that have met the definition for device success, excluding subjects with major protocol deviations such as:
 
 
▪ A major inclusion/exclusion criterion violation; or
 
▪ A major procedural deviation
 
 
The criteria for deviations meeting the classification of “major” will be defined before study endpoint data is available for statistical analysis. All major deviations will be adjudicated by an independent designee without visibility to study results.

Primary Efficacy Endpoint	
Primary patency defined as freedom from CEC adjudicated clinically-driven target lesion revascularization (CD-TLR) and freedom from core lab adjudicated duplex ultrasound derived binary restenosis at 12 months (defined as PSVR <math>\geq</math>2.5)

Primary Safety Endpoint	
Freedom from the occurrence of any new-onset major adverse event(s) (MAEs) defined as index limb amputation (above the ankle), CEC adjudicated clinically-driven target lesion revascularization (CD-TLR), or all-cause death at 30 days.

Procedure Start/End Time	
Start: The time of insertion of introducer sheath End: The time of withdrawal of last post-Tack PTA balloon catheter

Procedural Success	
Demonstrated vessel patency (<30% residual DS, by visual estimate) without the use of a bailout stent or the occurrence of MAE upon completion of the index procedure.

Renal Insufficiency	
An increase in serum creatinine of <math>\geq</math> 1.0 mg/dL over previous value requiring medical treatment but which does not require dialysis to resolve, or a serum creatinine level >2.5 mg/dL at baseline (subject should not be enrolled)

Restenosis	
Reoccurrence of narrowing or blockage or target lesion.

Rutherford Classification	Clinical scale identifying three grades of claudication and three grades of critical limb ischemia ranging from rest pain alone to minor and major tissue loss. (ACC/AHA PAD Practice Guidelines – Hirsch et al. 2005)
Class	Clinical Description
0	Asymptomatic
1	Mild claudication
2	Moderate claudication
3	Severe claudication
4	Ischemic rest pain
5	Minor tissue loss
6	Ulceration or gangrene

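### The AE reporting period opens when the Tack system enters the sheath, so events starting during access or angioplasty fall outside it, in conflict with the plan's procedure-wide AE items

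*Combined protocol and SAP*

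**What the plan says.** Section 14 fixes the start of safety reporting: "The adverse event (AE) reporting period will begin at the time of enrollment into the study". It refers the reader to Section 10.3.1, where a subject is "officially enrolled in the study once the Tack Endovascular System is advanced through the introducer sheath".

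The angioplasty comes earlier. Section 10.2, which labels it pre-enrollment, says: "All consented subjects undergoing balloon angioplasty for possible enrollment into this study shall receive PTA treatment". It also gives technique recommendations, for example: "Inflate the balloon and maintain inflation at the specified 1.1:1 diameter for a minimum of 60 seconds total".

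The procedure clock starts before both steps. The Section 19 entry for procedure start and end time reads: "Start: The time of insertion of introducer sheath".

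For subjects who turn out to be angiographic screen failures before or just after the angioplasty, Section 8.4 says: "No further follow-up will be required of these subjects, however; reason for angiographic failure shall be documented by the site into a screening log".

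**The concern.** Vascular access, contrast injection and balloon inflation all take place inside the index procedure but before the AE window opens. Several risks listed in Section 13.1, such as contrast reaction, embolism and abrupt closure, can begin in that interval. Section 14 nevertheless asks the investigator to grade each event by its relation to the study procedure as well as to the device. A procedure-related rate is then reported for a procedure whose first part lies outside the reporting period.

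Two things are at stake. The first is consistency. One site may report an angioplasty-phase event in an enrolled subject because the AE item for the index procedure seems to cover it, while another leaves it out because Section 14 excludes it. The second is the population that the safety results describe. A consented subject whose angioplasty goes badly enough to prevent Tack use contributes no AE data.

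**Working it through.** The plan states no figure on this point, so the check is a cross-reading.

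**1. Order of events in the index procedure**

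| Step | Source | Inside the procedure? | Inside the stated AE period? |
|---|---|---|---|
| Sheath insertion | Section 19, Procedure Start/End Time | Yes, it is the start | No |
| Baseline angiogram | 10.1 | Yes | No |
| Angioplasty | 10.2 | Yes | No |
| Post-angioplasty eligibility check | 10.2.1, 8.4 | Yes | No |
| Tack system through the sheath (enrollment) | 10.3.1 | Yes | Yes, it opens here |
| Post-dilatation and completion | 10.4 | Yes | Yes |

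**2. Text that points to procedure-wide capture**

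- Table 5 marks AE assessment in the Implant Procedure column.
- Section 10.4.2 lists AE occurrence among the items recorded when the index procedure is complete, with no limit on onset.
- Section 19 defines the index procedure as the whole interventional procedure in which the device is used.
- Section 14.1, in its list of events not counted as AEs, refers to the angioplasty and the Tack placement as one procedure.

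These items list an assessment but do not say when an event must begin to count. Section 14 is the only text that defines the period. The plan never says whether an event that began during angioplasty is an AE in a subject enrolled minutes later.

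**3. Subjects who are not enrolled after angioplasty**

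Section 8.4 provides a log entry and no follow-up. Section 7.5.4 makes acute or sub-acute thrombosis in the target lesion an exclusion, so a complication of the angioplasty can itself be the reason a subject leaves. No section provides AE collection for these subjects.

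**4. Reach into the primary safety endpoint (Section 16.8)**

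MAEs are counted over the 30 days after the index procedure, in ITT subjects. Taking the components in turn for an enrolled subject:

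- Death before Tack introduction cannot occur, because the subject would not have been enrolled.
- CD-TLR needs an ABI fall relative to the pre-discharge value (Section 19), so it cannot precede Tack introduction.
- Above-ankle amputation between sheath insertion and Tack introduction is not a realistic event.

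The safety sample size is also untouched. With 138 subjects, a goal of 88% and an assumed 95%, the exact rule needs at least 128 subjects free of MAE. P(X ≥ 128 | 138, 0.88) = 0.0493 and P(X ≥ 128 | 138, 0.95) = 0.914, consistent with the stated one-sided 5% and 90% power.

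**The case against.** The strongest defence is that the Tack is the investigational product. Section 8.2 screens patients who already need balloon angioplasty, Section 10.1.1 ties technique to institutional standard of care, and the balloons are standard or FDA-approved. The device cannot cause an event before it is introduced, and an AE period opening at introduction matches the ITT definition. This stands for device-relatedness. It does not answer procedure-relatedness, which Section 14 also collects.

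The defence is also right to resist several stronger readings:

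- A reader might infer that angioplasty complications are never recorded. The documents do not support that. The AE items in Table 5 and Section 10.4.2 can be read to cover the whole procedure in enrolled subjects, and a complication that first appears after Tack introduction is inside the period whatever its cause.
- A reader might infer that the angioplasty phase is unobserved. Section 10.2.1 records the number, type and length of dissections, the presence of thrombus, and inflation details, and Section 10.1 sends the index angiograms of all enrolled subjects to the core lab. These are angiographic descriptors, though. They are not AE reports with severity, relationship, outcome and reporting deadlines.
- A reader might infer that the DSMB cannot see this harm. Section 18.7.1 lets the board define which events it receives, in a charter that is not among these documents.
- Some minor access-site events, such as a hematoma under 5 cm, are excluded as AEs by Section 14.1 in any case.

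**Conclusion.** The point holds as a conflict between the stated AE period and the plan's own procedure-wide items, together with a gap for post-angioplasty screen failures. Procedure-related AE and SAE rates may be understated and may be captured differently across sites. The safety results describe subjects who reached Tack introduction, not all consented subjects who had the angioplasty.

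The size is unknown. It would be tempting to assume that 1% to 5% of the 210 subjects are affected, which gives about 2 to 10. The documents give no such rate, and that count would also assume that nothing is captured through Table 5 or Section 10.4.2, so no count is offered here. The documents give no number of post-angioplasty screen failures either.

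The primary 30-day MAE comparison in enrolled subjects is essentially unaffected. What is at issue is the descriptive AE tabulation and the population to which it refers. The conclusion assumes that sites take Section 14 as the governing definition at least some of the time.

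**What to change.** - In Section 14, start AE recording at introducer-sheath insertion of the index procedure for every subject who is then enrolled.
- Word Table 5 and Section 10.4.2 to match, so that all three give the same start.
- Add a field to the AE form for onset before or after Tack introduction, and tabulate pre-Tack events separately. Device-related rates then stay as they would be under the current start point.
- State in the clinical report that the safety results describe subjects who reached Tack introduction.

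The cost is a small amendment, one eCRF field, a few more AE forms and a slightly higher procedure-related event rate. Collecting SAEs in consented subjects who had the angioplasty but were not enrolled would go further, but it adds work in a group of unknown size, and the point does not depend on it.

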#### 14.1. ADVERSE EVENTS (AE)

An adverse event (AE) is any untoward medical occurrence, unintended disease or injury, or untoward clinical signs (including abnormal laboratory findings) in subjects, users or other persons, whether or not related to the investigational device/procedure.

For purposes of this study, the following events are not considered adverse events because they are normally expected to occur in conjunction with endovascular procedures / post-procedure, or are associated with customary, standard care of subjects undergoing these procedures:

- Early post-operative pain (within 24 hours post-index procedure) at the access site and/or related to position on procedure table
- Minor, localized tenderness, swelling, induration, bruising, oozing, hematoma <5 cm at vascular access site
- Post-anesthesia/conscious sedation emesis, nausea, or headache (within 24 hours post-index procedure)
- Chest pain without associated ECG changes
- Hematocrit decrease from baseline not associated with hemodynamic changes, remaining above 30% and not requiring transfusion
- Electrolyte imbalance without clinical sequelae following PTA/Tack procedure, even if requiring correction
- Low grade temperature increase ( $\leq 38^{\circ}\text{C}/\leq 101.4^{\circ}\text{F}$ )
- Sinus bradycardia/tachycardia that does not require treatment or intervention

- Systolic or diastolic blood pressure changes that do not require treatment or intervention
- Any pre-planned (planned prior to enrollment) surgical/endovascular procedures

This listing of events is intended to provide guidance to the investigational sites for purposes of adverse event reporting. The Investigator at the investigational site should utilize his/her own clinical judgment in evaluating adverse experiences, and may decide that the above events should be reported as adverse events.

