#### 14.3. SERIOUS ADVERSE EVENTS (SAE)

A serious adverse event (SAE) is defined an adverse event that:

- led to death,
- led to a serious deterioration in the health of the subject, that either resulted in:
- a life-threatening illness or injury, or
- resulted in a permanent impairment of a body structure or a body function, or

- required in-patient hospitalization or prolongation of existing hospitalization, or
- resulted in medical or surgical intervention to prevent life-threatening illness or injury or permanent impairment to body structure or a body function, or,
- led to fetal distress, fetal death or a congenital abnormality or birth defect.

Note: Planned hospitalization for a pre-existing condition, or a procedure required by the investigational plan without serious deterioration in health, is not considered a serious adverse event.

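### Section 14.1 removes listed events from the AE definition with no exception for seriousness, so a hospital admission for chest pain with a normal ECG is not reportable by default

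*Combined protocol and SAP*

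**What the plan says.** Section 14.1 defines an adverse event broadly and then takes a list of events out of the definition. The reason given is "because they are normally expected to occur in conjunction with endovascular procedures / post-procedure", or that they belong to customary care of these patients. Two items on the list are:

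- "Chest pain without associated ECG changes"
- "Hematocrit decrease from baseline not associated with hemodynamic changes, remaining above 30% and not requiring transfusion"

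Two other items carry an explicit limit of 24 hours: "Early post-operative pain (within 24 hours post-index procedure") and "Post-anesthesia/conscious sedation emesis, nausea, or headache (within 24 hours post-index procedure").

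The section closes by calling the list guidance. It tells the investigator to use clinical judgment and allows, but does not oblige, the reporting of a listed event.

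Section 14 starts the AE period at enrollment and says that it "will continue through study completion". Section 7.4 sets follow-up at 36 months, or 12 months for a subject who receives no Tack. Section 14.3 opens with "A serious adverse event (SAE) is defined an adverse event that" and then gives the criteria, in-patient hospitalization or its prolongation among them. Section 14.1.1 requires AEs to be assessed for ADE, SAE, MAE, SADE or UADE status.

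**The concern.** An exemption list for expected minor events is ordinary practice. The difficulty is where this one sits. It acts on the AE definition itself, and the seriousness assessment is built on that definition, so the exemption takes effect before anyone asks whether the event was serious. The 2-business-day report in Section 14.3.1 is then not due.

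Later review would not reliably recover such an event. The Medical Monitor (18.8) works from reported adverse events. The Clinical Events Committee (18.7.2) works from events that investigators report or that the sponsor refers. The DSMB (18.7.1) sees site-reported and adjudicated events. With up to 40 sites and a discretionary rule, the same admission could be an SAE at one site and unrecorded at another. Section 13.3 says the data are to support a Premarket Approval application, so the completeness of the SAE listing matters.

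**Working it through.** No arithmetic applies. The check has two parts: which limits each exempt item carries, and whether anything later in the reporting chain restores a serious event.

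**Limits on each item in the Section 14.1 list**

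| Item | Time window | Other limit |
|---|---|---|
| Access-site or positional pain | 24 hours | Site or cause |
| Emesis, nausea, headache | 24 hours | Due to anesthesia or sedation |
| Minor access-site reactions | None | Access site; hematoma under 5 cm |
| Chest pain | None | No ECG changes |
| Hematocrit fall | None | No hemodynamic change, above 30%, no transfusion |
| Electrolyte imbalance | After the procedure | No clinical sequelae |
| Low-grade temperature | None | Temperature ceiling |
| Sinus rate changes; blood pressure changes | None | No treatment or intervention needed |
| Pre-planned procedures | None | Planned before enrollment |

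Several items have no hour limit, so a missing window is not by itself unusual. What sets chest pain apart is that a single test result is its only limit. It has no window, no tie to the procedure or access site, and no condition on treatment or consequence. The hematocrit item shares the missing window, but each of its three conditions removes clinically important falls.

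**The reporting chain, for a subject admitted with chest pain and a normal ECG and no further diagnosis recorded**

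1. Section 14.1: the event is on the list, so it is not an AE unless the investigator chooses to report it.
2. Section 14.1.1: only AEs are assessed for seriousness, so no assessment is triggered.
3. Section 14.3: hospitalization is a listed criterion, but an SAE must first be an AE.
4. Sections 14.2 and 14.5: an ADE is an adverse event and an SADE is an ADE, so these routes are closed in the same way.
5. Section 14.4: MAEs are death, major amputation and clinically driven TLR. Chest pain is none of these.
6. Section 14.6: the UADE definition is not worded as a subset of AE. Section 13.1 already lists "Angina / coronary ischemia / myocardial infarction" as anticipated, so this route would not ordinarily apply.

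No sentence in Sections 14 to 14.6.1 makes reporting mandatory when a listed event meets a seriousness criterion.

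**Dependence on the time window.** The result does not need a late event. If the list is confined to the peri-procedural period, a stay prolonged on the day after the procedure by chest pain with a normal ECG still follows steps 1 to 6. The missing seriousness exception and the missing window are separate gaps, and the first remains on either reading.

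**The case against.** The strongest reply is that the list is guidance, that investigators are told to use judgment, and that the opening rationale ties it to the procedure. On that view chest pain months later falls outside the list. Monitors also compare the eCRF with source records (18.3), and the DSMB may define events for real-time reporting (18.7.1). Much of this stands. The procedural rationale is a fair ground for reading the list narrowly. It does not settle the matter, because the drafters wrote 24-hour limits for some items and not for these, and judgment that merely permits a report is no substitute for a rule on serious events.

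A reader might infer stronger points that the documents do not support:

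- *Serious bleeding goes unreported.* The hematocrit exemption needs all three of its conditions together, and gastrointestinal bleeding and hemorrhage other than minor access-site bleeding are not on the list. What remains is a fall that is serious only through, for example, hospitalization. Hematocrit is not among the baseline tests in Section 9.1 or the assessments in Table 5, so no scheduled follow-up value would bring the item into play.
- *The exemption is a 36-month rule.* That is a possible literal reading, reached by joining the missing window to the AE period. It is not stated.
- *Section 14.1 contradicts Section 13.1 or the MI definition in Section 19.* It does not. Section 13.1 lists anticipated risks for the consent discussion. A non-Q-wave MI established by enzymes is an MI and is reportable whatever the ECG shows. Section 14.1 exempts a symptom, not those diagnoses.

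**Conclusion.** The point holds in a limited form. As written, a listed event that meets an SAE criterion is not reportable by default, and the only override is discretionary. Chest pain is the item of real concern. The hematocrit item is a lesser one.

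The conclusion rests on the literal wording of Sections 14.1, 14.1.1 and 14.3 taken together, and on the case where no reportable diagnosis such as angina or MI is recorded alongside the symptom.

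The size cannot be given as a count, because the documents contain no rates for these events. The rule applies to up to 210 subjects. It does not touch the primary safety endpoint of death, major amputation or clinically driven TLR at 30 days. Overall AE and SAE rates enter neither primary hypothesis and are not among the observational endpoints in Section 6.2. What is affected is the completeness of the safety listings and of what the oversight bodies see. That justifies a correction, but it does not put the trial's main conclusions in doubt.

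**What to change.** Make two wording changes in Section 14.1.

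1. Add the sentence: *No event on this list is exempt if it meets any SAE criterion in Section 14.3.* The existing note in 14.3 on planned hospitalization would still keep pre-planned procedures out, so the sentence does not disturb that item.
2. Tie the chest pain and hematocrit items to a stated peri-procedural period, as the list already does for early pain, sedation effects and electrolyte imbalance. The sponsor should choose the period.

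The exception should not be widened to signs of any condition named in Section 13.1. That section includes pain, fever, hematoma, arrhythmia, blood pressure changes and anemia, so such a clause would cancel most of the list.

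The cost is a protocol wording change and a few more AE and SAE forms, mainly for short admissions or prolonged stays that prove benign.
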